7.1.2. Summary Measure

Difference between the two treatment groups (Q2M – BIK) in the proportion of participants with HIV-RNA ≥ 50 c/mL at Month 12 (OLI and BIK)/Month 11(D2I) (as defined by the US FDA snapshot algorithm) and its two-sided 95% confidence interval will be produced. Note for the Q2M arm, primary endpoint data from the Q2M OLI subjects at Month 12 and data from the Q2M D2I subject at Month 11 will be combined for demonstration of non-inferiority.

7.1.3. Population of Interest

The primary efficacy analyses will be based on the modified Intent-To-Treat Exposed (mITT-E) population, unless otherwise specified.

7.1.4. Strategy for Intercurrent (Post-Randomization) Events

As defined by the Snapshot algorithm, HIV-RNA ≥ 50 copies/mL is determined by the last available on-treatment HIV-1 RNA measurement within the analysis visit window of interest.

Participants without evaluable HIV-RNA data for the visit of interest and who discontinue treatment for reasons not related to adverse event while having HIV-1 RNA ≥ 50 copies/mL at time of discontinuation, or who change study treatment not permitted per protocol prior to the analysis window are classified as having HIV-RNA ≥ 50 copies/mL.

A “while on-treatment” strategy will be implemented when a Q2M subject becomes pregnant on study but is allowed to continue. Viral load data collected after confirmed pregnancy will not be evaluated for summary tables and statistical analysis in the primary analysis. Additional sensitivity analysis including all observed data may be performed to assess consistency. See [Appendix 13: Data Handling for Pregnant Subjects](#) for details.

7.1.5. Statistical Analyses / Methods

Details of the planned displays are provided in [Appendix 15: List of Data Displays](#) and will be based on GSK data standards and statistical principles.

Unless otherwise specified, endpoints / variables defined in Section 7.1.1 will be summarised using descriptive statistics, graphically presented (where appropriate) and listed.

7.1.5.1. Statistical Methodology Specification

Primary Statistical Analysis
Endpoint / Variables

 Proportion of participants with plasma HIV-RNA greater than or equal to 50 copies/mL at Month 12 (OLI and BIK)/Month 11 (D2I) per Snapshot algorithm for the mITT-E population.
Snapshot Dataset

 Virologic outcome (“HIV-RNA <50” or “≥ 50 c/mL”) per Snapshot algorithm is determined by the last available on-treatment HIV-1 RNA measurement within the analysis visit window of interest (refer to analysis window defined in Section 16.3). In addition, participants who discontinue for reasons not related to adverse event with on-treatment HIV-1 RNA result at the time of discontinuation ≥ 50 c/mL or who change study treatment not permitted per protocol during Maintenance Phase before the analysis visit are classified as ‘HIV-RNA ≥ 50 c/mL’. Full details of the Snapshot algorithm are provided in Appendix 9: Snapshot Algorithm Details
Model Specification

 The primary efficacy endpoint will be analysed using a stratified analysis with Cochran-Mantel-Haenszel (CMH) weights, adjusting for the randomization strata BMI (<30, ≥ 30 kg/m²) and Gender at Birth (female, male)

- The CMH estimate of the adjusted treatment difference will be calculated as a weighted average of strata-specific estimates of the treatment difference calculated within each stratum as follows:
 - Baseline BMI < 30 kg/m² and Male Gender at Birth
 - Baseline BMI < 30 kg/m² and Female Gender at Birth
 - Baseline BMI ≥ 30 kg/m² and Male Gender at Birth
 - Baseline BMI ≥ 30 kg/m² and Female Gender at Birth

- If n_k is the number of CAB LA + RPV LA (Q2M) treated participants, m_k is the number of BIK arm treated participants, and $N_k = n_k + m_k$ is the total number of participants in the k^{th} stratum, then the CMH estimate is given by

$$\hat{d}_{cmh} = \frac{\sum W_k \hat{d}_k}{\sum W_k}$$

where

$$W_k = \frac{n_k m_k}{N_k}$$

are CMH weights and \hat{d}_k are estimates of the differences in proportions between the two treatment arms, p_{Q2M} and p_{BIK} , for the k^{th} stratum.

- The corresponding two-sided 95% CI will be calculated as

$$\hat{d}_{cmh} \pm 1.96 \times \sqrt{\hat{\text{var}}(\hat{d}_{cmh})}$$

where the variance estimator [Sato, 1989] consistent in both sparse data and large strata is given below

$$\hat{\text{var}}(\hat{d}_{cmh}) = \frac{\hat{d}_{cmh} (\sum P_k) + \sum Q_k}{(\sum n_k m_k / N_k)^2} = \frac{\hat{d}_{cmh} (\sum P_k) + \sum Q_k}{(\sum W_k)^2}$$

where

$$P_k = \frac{n_k^2 y_k - m_k^2 x_k + n_k m_k (m_k - n_k) / 2}{N_k^2}$$

$$Q_k = \frac{x_k (m_k - y_k) / N_k + y_k (n_k - x_k) / N_k}{2}$$

with x_k and y_k corresponding to the number of participants with Plasma HIV-1 ≥ 50 c/mL at Month 12 (OLI and BIK)/Month 11 (D2I) per FDA Snapshot for the Q2M and BIK arm, respectively, for the k^{th} stratum.

Model Results Presentation

 • Adjusted CMH estimate of the difference in the proportion of participants with "HIV-1 RNA ≥ 50" between each treatment group (Q2M – BIK) and corresponding 95% confidence interval. • Non-inferiority will be concluded if the upper bound of the two-sided 95% confidence interval (CI) for the CMH adjusted difference in proportion of participants with 'HIV-1 RNA≥ 50' in the CAB LA + RPV LA (Q2M) group minus proportion of participants with 'HIV-1 RNA≥ 50' in the BIK group is less than 4%. • If the analysis shows non-inferiority, then a superiority hypothesis will be tested at the two-sided 5% level of significance. Superiority favoring CAB LA + RPV LA (Q2M) will be declared if the upper limit of the confidence interval is below 0% for the mITT-E population analysis. If superiority is declared, the p-value for superiority will also be calculated.
Subgroup Analyses

 • Treatment Heterogeneity across randomization strata: 
 ○ The weighted least squares chi-squared statistic [Fleiss, 1981] will be used to test for one-way homogeneity across the levels of each categorical variable, with each categorical variable considered separately. ○ Following Lui and Kelly [Lui, 2000] $\frac{1}{2}$ will be added to each cell in any strata for which the stratum-specific rate estimates of either p_{Q2M} or p_{BIK} are zero or one, and tests will be one-sided. ○ Any heterogeneity found to be statistically significant will be explored and if necessary, results will be reported for each level of the categorical variable. Investigation of heterogeneity will be confined to the primary endpoint. Tests of homogeneity will be assessed at the one-sided 10% level of significance.
CCI
Sensitivity Analyses

 • Per-Protocol population analysis: To assess the impact of important protocol deviations, statistical analysis will be repeated using the Per-Protocol population and compared for consistency with the results from the primary mITT-E population analysis.

- All Data as Observed:
This analysis will include all observed data including those collected after confirmed pregnancy, in the mITT-E population.
- Efficacy Sensitivity:
This analysis will be based on the ITT-E population at Month 12.

7.2. Secondary Efficacy Analyses

7.2.1. Endpoint / Variables

The key secondary efficacy endpoint is proportion of participants with plasma HIV-1 RNA <50 c/mL (c/mL) at Month 12 (OLI and BIK)/Month 11(D2I) using the FDA Snapshot algorithm.

Other secondary efficacy endpoints are listed below:

- Proportion of participants with plasma HIV-1 RNA <50 c/mL (c/mL) at Month 6 (OLI and BIK)/Month 5 (D2I).
- Proportion of participants with plasma HIV-1 RNA \geq 50 c/mL (c/mL) at Month 6 (OLI and BIK)/Month 5(D2I)
- Proportion of participants with protocol-defined confirmed virologic failure (CVF) through Month 6 and Month 12 (OLI and BIK)/Month 5 and Month 11 (D2I).
- Changes from Baseline in viral load and CD4+ cell count over time including Month 6 and Month 12 (OLI and BIK)/Month 5 and Month 11 (D2I)

7.2.2. Summary Measure

Binary endpoints: difference in the proportion of participants with HIV-RNA \geq 50 c/mL (or < 50 c/mL) as defined by the US FDA snapshot algorithm at specified time point between treatment groups (Q2M – BIK) will be produced.

Continuous endpoints (e.g. CD4+ cell count): descriptive summary statistics per GSK data standards will be produced.

7.2.3. Population of Interest

The secondary efficacy analyses will be based on the Intent-to-Treat Exposed (ITT-E) population, unless otherwise specified. Note in the Month 12 analysis, mITT-E will be used in summary tables.

7.2.4. Strategy for Intercurrent (Post-Randomization) Events

As defined by the snapshot algorithm, only participants with last available HIV-1 RNA measurement less than 50 c/mL while the participant is on treatment within the analysis visit window of interest are classified as HIV-1 RNA < 50 c/mL.

A “while on-treatment” strategy will be implemented as described in Section 7.1.4. Same approach will be applied to efficacy tables for protocol-defined confirmed virologic failure (CVF) and CD4+ cell count. Data after confirmed pregnancy will not be evaluated for the summary tables unless otherwise noted, but will be included in the listings if applicable.

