Extension Switch (ES)	
 All randomized subjects from BIK arm who receive at least one dose of CAB and/or RPV during the Extension Phase of the study. Participants will be assessed according to actual treatment received during the Extension Phase. 	
 Safety and efficacy for BIK subjects switching to Extension Q2M if applicable

Population	Definition / Criteria	Analyses Evaluated
Pharmacokinetic (PK)	
 All participants who receive CAB and / or RPV and undergo PK sampling during the study and provide evaluable CAB and / or RPV plasma concentration data with at least 1 non-missing PK assessment (Non-quantifiable [NQ] values will be considered as non-missing values). Note: PK samples that may be affected by protocol deviations will be reviewed by the study team to determine whether or not the sample will be excluded. 	
 PK (Pregnant subjects on Q2M arm only for this RAP)
Confirmed Virologic Failure (CVF)	
 All participants in the ITT-E population who met Confirmed Virologic Failure (CVF) CVF during the Maintenance and/or Extension Phases is defined as: Rebound as indicated by two consecutive plasma HIV-1 RNA levels ≥ 200 c/mL (Day 1 values not applicable) after prior suppression to < 200 c/mL 	
 Virology Efficacy
Modified Confirmed Virologic Failure (mCVF)	
 All participants in the mITT-E population who met Confirmed Virologic Failure (CVF) Note this population is only applicable to summary tables 	
 Virology Efficacy
Long-term Follow-up (LTFU)	
 Discontinued subjects who have received at least one dose of CAB LA and/or RPV LA and have met any of the following criteria: 
 have at least one Long-term Follow-up phase clinic visit, have filled out the LTFU phase conclusion form, or have indicated the continuation to LTFU phase in the subject continuation form. 	
 Safety

Refer to [Appendix 15](#): List of Data Displays which details the population used for each display.

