5.5.1. Primary Analysis

The primary comparison of interest is the comparison between CAB LA + RPV LA (Q2M) and BIK for the primary endpoint in the mITT-E population at Month 12 (OLI and BIK)/Month 11 (D2I). The primary comparison will be made at a one-sided 2.5% level of significance. Treatment with CAB LA + RPV LA (Q2M) will be declared non-inferior to BIK if the upper bound of a two-sided 95% confidence interval for the difference (Q2M – BIK) in proportion of participants with HIV-1 RNA ≥ 50 c/mL is below 4%.

If the primary analysis demonstrates non-inferiority, then a superiority hypothesis will be tested at the two-sided 5% level of significance. Superiority favoring CAB LA + RPV LA (Q2M) will be declared if the upper limit of the confidence interval is below 0% for the mITT-E population analysis. If superiority is declared, the p-value for superiority will also be calculated.

No multiple comparison adjustment is necessary for testing non-inferiority followed by superiority (conditional on achieving significance in the non-inferiority test) since testing follows a pre-specified sequence of hypothesis such that if the first hypothesis tested is not significant, all subsequent tests will not be performed. This fixed sequence procedure controls the type I error rate at the nominal level.

Subjects who became pregnant during the study will be allowed to continue CAB LA + RPV LA (Q2M) treatment, while those who became pregnant on BIK will be withdrawn. To minimize bias, a “while on-treatment” strategy will be implemented. Viral load data collected after confirmed pregnancy will not be evaluated for summary tables and statistical analysis in the primary analysis (see [Appendix 13: Data Handling for Pregnant Subjects](#)).

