16.10. Appendix 10: Variables Defined for Time to Event Analysis

Programming Instructions for the Kaplan-Meier analysis of treatment-related discontinuation equals failure (TRDF)		
Condition	Censor Status	Event Description/AVAL
1. Participant met CVF event criteria during the Maintenance Phase (based on derived CVF)	CNSR=0	EVNTDESC=CVF AVAL=Study Day of SVF* *immediately preceding CVF
2. Participant with Maintenance Phase withdrawal due to ' Lack of Efficacy ', ' Treatment Related AE ', ' Intolerability due to Injection ', or ' Protocol Defined Safety Stopping Criteria ' during Maintenance Phase Note: primary reason and/or standardized subreason for discontinuation based on Maintenance Conclusion form in the eCRF. ' Protocol Defined Safety Stopping Criteria ' includes GSK defined liver chemistry stopping criteria, renal toxicity criteria and QTc withdrawal criteria. Treatment Related AE' is defined as participants who have primary reason for withdrawal =AE and who have at least one AE considered drug related and leading to withdrawal/permanent discontinuation of investigational product.	CNSR=0	EVNTDESC= terms in italic , respectively. For Q2M arm: AVAL= min [Study Day of Maintenance Phase Discontinuation, Study day of Starting LTFU HAART if applicable, max(Study Day of Last Maintenance Q2M IM Dose + 67, Study Day of Last Maintenance Oral Dose + 1)] For BIK arm: AVAL= min [Study Day of Maintenance Phase Discontinuation, Study Day of Maintenance IP Stop Date + 1] Note: 
 • Last Q2M IM / last oral dose/ Maintenance IP Stop Date only applies to subjects who permanently discontinue from study treatment. • Date of Maintenance Phase discontinuation is from the Maintenance Phase Conclusion form in the eCRF.
If none of the above conditions met		
3. Participant with Maintenance Phase withdrawal due to other reasons	CNSR=1	EVNTDESC='Censored due to Study Discontinuation for Other Reasons' AVAL will be defined as the same as above 2
4. Participant who did not have premature withdrawal from the Maintenance Phase	CNSR=1	EVNTDESC='Censored due to data cutoff for analysis'

Programming Instructions for the Kaplan-Meier analysis of treatment-related discontinuation equals failure (TRDF)		
Condition	Censor Status	Event Description/AVAL

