16.13. Appendix 13: Data Handling for Pregnant Subjects

The SOLAR study allows pregnant subjects on the Q2M arm to continue CAB LA + RPV LA treatment, while those who became pregnant on the BIK arm will be withdrawn. To minimize bias, for summary tables, if Q2M subjects continue while being pregnant, data after date of confirmed pregnancy (as recorded in the eCRF EOS pregnancy form) will not be evaluable for pregnant Q2M subjects with documented evidence confirming pregnancy unless the confirmation occurs prior to or on the same day as termination of pregnancy (as recorded on the EOS pregnancy form and the AE form, respectively) within the same time period between two study visits. The above data handling strategy will not be implemented on the following:

- All adverse events
- ECG/QTc analysis
- Vital signs
- eC-SSRS
- [REDACTED]
- Health Outcomes
- Virology

Note all observed data collected for all pregnant subjects will be included in the listings.

For study outcomes based on the FDA snapshot algorithm, an additional sub-category will be added under “No Virologic Data”: Not evaluated or discontinued due to confirmed pregnancy. Viral load after confirmed pregnancy of a Q2M subject will not be evaluated for snapshot outcomes (See [Appendix 9: Snapshot Algorithm Details](#)).

Sensitivity analysis including all data (all data as observed) will be provided for the following snapshot-based analysis is applicable:

- Summary of Study Outcomes (50 c/mL threshold)
- Summary of Analysis for Proportion of Subjects with Plasma HIV-1 RNA ≥ 50 c/mL (or < 50 c/ml)
- Proportion of Subjects with Plasma HIV-1 RNA ≥ 50 c/mL (or < 50 c/ml) by Visit

If no Q2M subject became pregnant on study, then the “while on-treatment” strategy will not be necessary and therefore no sensitivity analysis will be performed, and the additional sub-category mentioned above will not be needed.

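### Appendix 10's Kaplan-Meier rules do not carry out the pregnancy cut-off that Section 7.2.4 sets for confirmed virologic failure, and they leave the two arms handled differently after pregnancy

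*SAP*

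**What the plan says.** Section 5.5.1 sets out the difference between arms: participants who become pregnant on Q2M are "allowed to continue CAB LA + RPV LA (Q2M) treatment, while those who became pregnant on BIK will be withdrawn". The plan answers this with a while-on-treatment strategy. For the secondary endpoints, Section 7.2.4 states: "Same approach will be applied to efficacy tables for protocol-defined confirmed virologic failure (CVF"), and likewise for CD4+ cell count. It adds: "Data after confirmed pregnancy will not be evaluated for the summary tables unless otherwise noted". Listings keep the data.

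Appendix 10 (Section 16.10) gives the programming rules for the two Kaplan-Meier analyses: treatment-related discontinuation = failure (TRDF, Table 2.25) and efficacy-related discontinuation = failure (ERDF, Table 2.26).

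- Condition 1 is an event: "Participant met CVF event criteria during the Maintenance Phase (based on derived CVF").
- Condition 2 makes certain withdrawals events. Lack of efficacy counts in both analyses. Treatment-related adverse events, injection intolerability and safety stopping criteria count in TRDF only.
- Condition 3 censors withdrawals for any other reason at discontinuation or end of treatment.
- Condition 4 covers the "Participant who did not have premature withdrawal from the Maintenance Phase". For Q2M, censoring is at the earliest of the Month 13 (D2I)/14 (OLI) visit, the start of long-term follow-up HAART, last contact, and the end of treatment coverage for those who stopped permanently.

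The date of confirmed pregnancy appears in none of the four conditions.

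Appendix 13 (Section 16.13) exempts virology, among other outputs, from the pregnancy rule. It limits the all-data check: "Sensitivity analysis including all data (all data as observed) will be provided for the following snapshot-based analysis". No CVF or Kaplan-Meier output is on that list. Section 4 defines the CVF population as "All participants in the ITT-E population who met Confirmed Virologic Failure (CVF") and the mCVF population likewise within mITT-E, neither with a pregnancy exclusion.

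**The concern.** The plan sets a rule for CVF after pregnancy and then gives derivation steps that do not contain it. A programmer working on Tables 2.25 and 2.26 has to choose. Following Appendix 10 to the letter counts a failure that Section 7.2.4 says is not evaluated. Following Section 7.2.4 removes the failure but leaves the participant in the risk set, apparently failure-free, during time in which a CVF cannot be recorded. A BIK participant in the same position leaves the risk set at withdrawal.

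At stake is the coherence of two supportive analyses of a secondary endpoint. A failure on continued injections during pregnancy could be shown as event-free follow-up, and no summary table would give the CVF result with it included.

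**Working it through.** **Rule trace.** The cases below set Section 7.2.4 against Appendix 10.

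| Case | Rule reached | Result in Tables 2.25 and 2.26 |
|---|---|---|
| Q2M, pregnant, continues, later CVF, Appendix 10 read alone | Condition 1 | Event, against Section 7.2.4 |
| Same participant, Section 7.2.4 applied to Condition 1 | Condition 4 | Event-free and at risk up to the Month 13/14 visit |
| Q2M, pregnant, continues, later withdraws for lack of efficacy | Condition 2 | Event in TRDF and ERDF, unless the cut-off is also meant to apply here, which is not stated |
| BIK, pregnant | Condition 3 | Censored at discontinuation |

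The Snapshot algorithm in Appendix 9 handles the same situation consistently. It puts Q2M participants not evaluated because of pregnancy, and participants withdrawn because of pregnancy, into one category under no virologic data. Appendix 10 has no counterpart.

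**Crude proportion.** Table 2.29 is a cumulative proportion in mITT-E. After pregnancy both participants stay in the denominator and neither can add a CVF, so the arms are handled alike.

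**Size of one uncounted event.** The SAP states no figure that depends on this rule, so there is nothing to reproduce. The inputs are about 654 randomised 2:1 (Section 2.3).

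- Q2M participants: 654 × 2/3 = 436.
- One event: 1/436 = 0.23 percentage points.
- mITT-E drops 11 participants (Section 2.1), with no split by arm given. If all 11 were on Q2M, 1/(436 − 11) = 1/425 = 0.24 points.

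**Illustrative product-limit estimate.** S(t) = Π(1 − d_i/n_i), read at day 361. The following are assumptions, not SAP figures: 436 Q2M participants; two counted CVFs at day 120 and one at day 300; one pregnancy confirmed at day 180; one possible later CVF at day 270.

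- Kept at risk, later CVF not counted: (434/436) × (433/434) = 433/436, so failure is 0.6881%.
- Censored at day 180: (434/436) × (432/433), so failure is 0.6886%.
- Later CVF counted: (434/436) × (433/434) × (432/433) = 432/436, so failure is 0.9174%.

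Leaving the event out lowers the estimate by 0.9174 − 0.6881 = 0.2293 points. The choice of censoring date alone moves it by 0.6886 − 0.6881 = 0.0005 points. With five pregnancies instead of one, the censored version is (434/436) × (428/429), failure 0.6907%, a shift of about 0.003 points. Repeating this with five or nine counted CVFs gives the same differences to this precision. Two uncounted events give 0.46 points.

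If there is no CVF after pregnancy, keeping her at risk gives the same estimate as counting all data.

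**The case against.** The strongest reply is that Appendix 10 does not itself make anyone failure-free. Condition 1 has no pregnancy cut-off, so read alone it counts her failure, and Condition 2 counts a withdrawal for lack of efficacy in both analyses. That stands. The defect is an unreconciled conflict between two sections, and a post-pregnancy failure need not be lost from the Kaplan-Meier results.

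A reader might infer that the CVF proportion itself is biased towards Q2M. The documents do not support this: Table 2.29 treats the arms alike after pregnancy, and the stated aim of the rule is to reduce bias.

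A reader might also infer that the virology tables contradict the efficacy tables. They may show different counts, but Section 7.2.4 allows for noted exceptions and Appendix 13 names virology as one. That is a declared difference of scope. Only Table 2.30 is unclear: it sits among the efficacy tables but uses mCVF, and the plan does not say whether Section 7.2.4 governs it.

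Nor would such a failure be hidden. Listing 31 covers all CVF participants, Listing 32 shows HIV-1 RNA with the pregnancy confirmation date, and Listing 64 gives resistance data. This lowers the stakes but supplies no summary estimate.

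Finally, the tables are read at Month 12 (OLI and BIK)/Month 11 (D2I), so follow-up beyond that, up to Month 13/14, cannot change those estimates. Censoring at pregnancy also barely moves them and does not restore an uncounted event. Both points are right. The censoring change makes the rules coherent and aligns the arms; the all-data tables show the effect of the missing event.

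**Conclusion.** The point holds as a gap between Section 7.2.4 and Appendix 10. Taken together, the two rules let non-evaluable time count as failure-free for Q2M while BIK is censored at withdrawal. Tables 2.25 and 2.26 could favour Q2M by about 0.23 percentage points per uncounted event, compared with counting it. That needs three things together: a Q2M participant who continues after confirmed pregnancy, a later CVF, and no withdrawal for lack of efficacy that is counted under Condition 2. The SAP gives no number for any of these, and 436 rests on the planned total and allocation.

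Without such an event the effect is negligible: at most about 0.003 points from the censoring date in the illustration, and none if no Q2M participant becomes pregnant. The primary Snapshot endpoint is not affected. This is a minor but worthwhile correction.

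**What to change.** - In Appendix 10, censor a Q2M participant with confirmed pregnancy and no earlier event at the confirmation date. Apply the same cut-off to Condition 1 and Condition 2 events, for both TRDF and ERDF.
- Add all-data-as-observed versions of Tables 2.25, 2.26 and 2.29, required only if there is a confirmed Q2M pregnancy, as already planned for Table 2.4.
- State whether Table 2.30 follows Section 7.2.4, and footnote any difference between the efficacy and virology CVF counts.

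The cost is a few lines of SAP wording and up to three conditional tables. No new data are needed.
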